#### **8.1.2. Sensitivity Analyses of the Primary Efficacy Endpoint**

The following sensitivity analyses will be performed, based on the CMH test as described in [Section 8.1](#):

- The primary efficacy endpoint analysis, repeated on Cohort 2 subjects in the ITT and PP populations on nonimputed data; and
- The primary efficacy endpoint analysis (excluding the CMH testing), repeated on Cohort 1 subjects in the All Treated population on nonimputed data only.

## 8.2. Secondary Efficacy Analysis

All secondary efficacy analyses will be performed using the All Treated population for subjects in Cohort 1 and the ITT population for subjects in Cohort 2, unless otherwise specified.

The statistical comparisons for all secondary efficacy endpoints for Cohort 2 subjects will be as follows:

- ARQ-252 cream 0.3% BID versus vehicle cream (all dose frequencies)
- ARQ-252 cream 0.3% QD versus vehicle cream (all dose frequencies)
- ARQ-252 cream 0.1% QD versus vehicle cream (all dose frequencies)
- ARQ-252 cream (all strengths and dose frequencies) versus vehicle cream (all dose frequencies)
- ARQ-252 cream 0.3% (all dose frequencies) versus vehicle cream (all dose frequencies)

### 8.2.1. Investigator Global Assessment (IGA)

Secondary efficacy endpoints relating to the IGA include the following:

- The rate of achievement of IGA of “clear” or “almost clear” PLUS at least a 2-point improvement from Baseline at Weeks 2, 4, 8, 12, and 13
- The rate of achievement of at least a 2-point improvement from baseline at Weeks 2, 4, 8, 12, and 13
- The rate of achievement of IGA of “clear” or “almost clear” at Weeks 2, 4, 8, and 13
- Change in IGA score at Weeks 2, 4, 8, 12, and 13 as compared to baseline

#### Rate of Achievement Analyses

Rate of achievement analyses will be performed using the same CMH test as described in [Section 8.1](#) as follows:

- The rate of achievement of IGA of “clear” or “almost clear” PLUS at least a 2-point improvement from baseline will be analyzed on Cohort 2 subjects in the ITT population (imputed and nonimputed data) and PP population (nonimputed data only);
- The rate of achievement of at least a 2-point improvement from baseline will be analyzed on Cohort 2 subjects in the ITT population (imputed and nonimputed data); and
- The rate of achievement of IGA of “clear” or “almost clear” will be analyzed on Cohort 2 subjects in the ITT population (imputed and nonimputed data) and PP population (nonimputed data only).

Rate of achievement of IGA success (IGA score of “clear” or “almost clear” plus at least a 2-point improvement from baseline) will also be analyzed by baseline IGA score, for Cohort 2 subjects in the ITT population (imputed and nonimputed data). The proportion of subjects achieving IGA success at Week 12 will be presented by study site for Cohort 2 subjects in the ITT population (nonimputed data only). Additionally, a summary will be provided for subjects in

Cohort 1 in the All Treated population (nonimputed data only), however, this will not include the CMH test.

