4.7 Selection of Study Population

4.7.1 Inclusion Criteria

Subjects must fulfill all of the following inclusion criteria to be eligible for participation in the study:

1. Participants legally competent to sign and give informed consent.
2. Males and females 18 years of age and older (inclusive) at the time of consent.
3. Clinical diagnosis of chronic hand eczema, defined as hand eczema persistent for more than 3 months, or returned twice or more within the last 12 months (Diepgen 2009). Generally stable disease for 6 weeks. Both irritant and non-irritant etiologic forms are allowed. All morphologic types are allowed, e.g., vesicular/dyshidrotic, hyperkeratotic, nummular, and other types.
4. An Investigator's Global Assessment of disease severity (IGA) of at least Mild ('2') at Baseline (Visit 2). (In Cohort 2, subjects with IGA of 'Mild' will be limited to 20% of total enrollment, and subjects with IGA of 'Severe' subjects will also be limited to 20% of total enrollment).
5. Chronic hand eczema involving at least 0.3% body surface area total (i.e., approximately a third of one handprint) lesions on both hands added together at Baseline (Visit 2).
6. Female subjects of childbearing potential (FOCBP) must have a negative serum pregnancy test at Screening and negative urine pregnancy test at Baseline (Visit 2). For FOCBP involved in any sexual intercourse that could lead to pregnancy: the subject must agree to use a highly effective contraceptive method for at least 4 weeks prior to Day 1. Additionally, from Day 1 until at least 4 weeks after the last investigational product administration, these subjects must agree to use at least 1 highly effective contraceptive method in addition to 1 barrier method according to Contraception Requirements (Figure 1).
7. Females of non-childbearing potential must either be post-menopausal with spontaneous amenorrhea for at least 12 months (post-menopausal status will be confirmed with FSH testing) or have undergone surgical sterilization (permanent sterilization methods include hysterectomy, bilateral oophorectomy, hysteroscopic sterilization, or bilateral salpingectomy) according to Contraception Requirements (Figure 1).
8. Males, if engaging in sexual intercourse with a female who is pregnant or a female of childbearing potential, must agree to use a condom every time during the study and every time subsequently until 4 weeks after the last investigational product administration.

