### **3.2. Sample Size and Power**

Cohort 1 will include approximately 6 evaluable subjects, which is deemed adequate for the purpose of evaluating safety and PK before Cohort 2 commences.

There are approximately 215 subjects planned for Cohort 2. The primary statistical comparisons will be to assess the ARQ-252 cream 0.3% BID group versus the vehicle BID group, to assess the ARQ-252 cream 0.3% QD group versus the vehicle QD group, and to assess the ARQ-252 cream 0.1% QD group versus the vehicle QD group. A sample size of 55 per active arm and 28 per vehicle arm will provide approximately 85% power at the 2-sided 10% significance level to detect a difference in the rate of subjects attaining an IGA score of clear or almost clear (for each ARQ-252-treated group versus vehicle group within the same daily dosing frequency), assuming an active treatment response rate of 45% and a vehicle response rate of 15%. For testing each active arm of 55 subjects versus the combined vehicle arms of 56 subjects, this sample size provides over 90% power for the comparison of the rate of subjects attaining an IGA score of clear or almost clear. This is based on a 2-group X2 test of equal proportions (without continuity correction).

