**Step 2:**

```
proc mi data=example_1 seed=88734121 nimpute=XX out=example_2;  
  class <treatment> <site>;  
  monotone regpmm(<baseline score> ..... <visit12 score>);  
  var <treatment> <site> <baseline score> ..... <visit12 score>;  
run;
```

XX will be the determined based on the proportion of missing data across visits.

**Step 3:** This step involves running CMH test stratified by baseline IGA score and site on each completed dataset and combining the results using PROC MIANALYZE.

```
proc freq data=example noprint;  
  by <imputationnumber> <visit> ;  
  tables <site> * <BL IGA> * <treatment> * <outcome> / cmh alpha=0.1;  
  output out=example_stat cmh;  
run;
```

In order to apply PROC MIANALYZE, normalizing transformations have to be applied to odds ratio. *P* values are obtained using Wilson Hilferty transformation as illustrated (Ratitch 2013).

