### 6.1.6. Pooling of Sites

Sites will be pooled for statistical analysis as follows. For analysis, sites should have a minimum of 10 randomized subjects. The smallest sites will be grouped sequentially in order of smallest to largest within each country, restricting to those sites that did not meet the minimum enrollment of 10, until each pooled site has a minimum of 10 subjects within each country with at least 1 subject in each treatment group.

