Odds Ratio (95% CI) [3]	X.XX (X.XX, X.XX)	X.XX (X.XX, X.XX)	X.XX (X.XX, X.XX)	X.XX (X.XX, X.XX)	
P value [3]	X.XXXXX	X.XXXXX	X.XXXXX	X.XXXXX	

Continue for Weeks 4, 8, 12, and 13.

Abbreviations: BID = twice daily; CI = confidence interval; IGA = investigator global assessment; QD = once daily.  
Note: The success scores were summarized using observed dataset. The odds ratio and P values were summarized using multiple imputation dataset. Separate multiple imputation steps were used for monotone and non-monotone missing data. For monotone missing pattern, a predictive mean matching model was used to impute missing value for a subject at particular visit having IGA score at previous study visit, treatment group, and pooled site group as independent variables and outcome at study visit as dependent variable. For non-monotone missing IGA values, Markov-Chain Monte Carlo (MCMC) method was used to impute the data at intermediate visits to make the missing data pattern into monotone before applying the predictive mean matching multiple imputation algorithm. Percentages are n/Number of subjects in the ITT population within planned treatment at each visit and subgroup\*100. Baseline is the last non-missing measurement taken on or before the day of first application of study drug.

[1] IGA Success plus  $\geq 2$ -point Improvement from Baseline (“Yes”) is defined as an IGA score of “Clear” or “Almost Clear” plus a  $\geq 2$ -grade improvement from baseline; “No” otherwise.

[2] 90% and 95% CIs for “Yes” are obtained using Wilson method.

[3] The odds ratio, 90% and 95% CIs, and P value are obtained from Cochran Mantel Haenszel test (stratified by pooled site group) comparing: ARQ-252 cream 0.3% QD vs vehicle cream (all dose frequencies); ARQ-252 cream 0.3% BID vs vehicle cream (all dose frequencies); and ARQ-252 cream 0.1% QD vs vehicle cream (all dose frequencies).  
Reference Listing: 16.2.6.1

Table 14.2.1.3.4  
Cohort 2, Pooled Treatments: Summary of Investigator Global Assessment (IGA) Success (Score of “Clear” or “Almost Clear” plus  $\geq 2$ -point Improvement from Baseline) by Study Visit and Baseline IGA Score – Multiple Imputation  
Categorical Results  
ITT Population

Study Visit Category/Statistic	Cohort 2		
	ARQ-252 Cream (All Strengths/Dose Frequencies) (N=XX)	ARQ-252 Cream 0.3% (All Dose Frequencies) (N=XX)	Vehicle Cream (All Dose Frequencies) (N=XX)
Week 2	XX	XX	XX
IGA Success [1]			
Yes	XX (XX.X%)	XX (XX.X%)	XX (XX.X%)

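### Keeping pooled-site strata inside the Mild and Severe subgroups often leaves the by-baseline-IGA odds ratio uncomputable, and pulls it towards 1 where it can be computed

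*SAP*

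**What the plan says.** SAP section 8.2.1 (Rate of Achievement Analyses) states that IGA success "will also be analyzed by baseline IGA score, for Cohort 2 subjects in the ITT population (imputed and nonimputed data"). The shells are Tables 14.2.1.3.3 and .4 (imputed) and .9 and .10 (observed). In all four, footnote [3] says that the odds ratio, intervals and P value are "obtained from Cochran Mantel Haenszel test (stratified by pooled site group) comparing" each active group with vehicle pooled over both frequencies. Baseline IGA is dropped as a stratum because it defines the subgroup. Site is kept.

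Three other provisions matter:
- **Subgroup size.** Protocol section 4.7.1 states that "subjects with IGA of 'Mild' will be limited to 20% of total enrollment" and sets the same limit for Severe.
- **Number of strata.** SAP section 6.1.6 requires that "sites should have a minimum of 10 randomized subjects", pooling small sites within country until that is met and every treatment group is represented.
- **Imputation.** SAP section 6.1.4, Step 3, says "normalizing transformations have to be applied to odds ratio" before the results are combined. It gives no rule for a dataset whose odds ratio is zero, infinite or undefined. The observed-data shells (.9, .10) define NE as not estimable. The imputed shells (.3, .4) do not.

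**The concern.** A stratum that holds only one treatment group, or only one outcome, adds nothing to a Mantel-Haenszel odds ratio. With about 24 subjects spread over a dozen or more site groups, many strata are like that. The estimate can then be zero, infinite or undefined although both arms have responders and non-responders overall.

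Most failures are infinite values, which arise when no vehicle responder shares a site group with an active non-responder. Reporting only the finite results therefore leaves out many of the most favourable ones, and the remainder sit nearer 1.

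The sponsor added this analysis (SAP section 10) to look at the effect by severity. An odds ratio near 1 in Mild or Severe could be read as a weak effect in those patients when it reflects the strata.

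**Working it through.** **The plan's own figure.** The plan gives no operating characteristic for these tables. Its nearest figure is the power in SAP section 3.2, "approximately 85% power at the 2-sided 10% significance level", for 55 v 28 subjects at 45% v 15%. The stated chi-square test without continuity correction gives 89.3%, so the plan errs on the safe side. This does not bear on the subgroup tables, but it supplies the only documented response rates.

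**Subgroup sizes at the cap** (Protocol 4.7.1; arm sizes from SAP 3.4). 0.20 × 215 = 43 subjects in each of Mild and Severe:
- each 0.3% arm: 0.20 × 61 = 12.2
- 0.1% QD: 0.20 × 31 = 6.2
- pooled vehicle: 0.20 × 62 = 12.4
- both 0.3% arms: 0.20 × 122 = 24.4
- all active: 0.20 × 153 = 30.6

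Because 20% is a cap, these are maxima. Moderate then holds about 0.60 × 61 = 37 per 0.3% arm.

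**Number of strata.** 215/10 allows at most 21 pooled groups. Simulating the section 6.1.6 rule with 45 sites gave about 13–16 on average. A range of 12–18 is used here as an assumption.

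**Estimator.** With active responders a, active non-responders b, vehicle responders c and vehicle non-responders d in stratum k of size n:

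OR = Σ(a·d/n) / Σ(b·c/n)

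The log odds ratio is not finite if either sum is 0.

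**Without site strata** the probability is exact: 1 − [1 − (1−pV)^nV − pV^nV] × [1 − (1−pA)^nA − pA^nA].
- 45% v 15%, 12 v 12: 0.85^12 = 0.142 and 0.55^12 = 0.001, giving 14%.
- 45% v 15%, 6 v 12: 0.55^6 + 0.45^6 = 0.036, so 1 − 0.858 × 0.964 = 17%.
- 25% v 8%, 12 v 12: 0.92^12 = 0.368 and 0.75^12 = 0.032, so 1 − 0.632 × 0.968 = 39%.
- 25% v 8%, 6 v 12: 0.75^6 = 0.178, so 1 − 0.632 × 0.822 = 48%.

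**With 12–18 site strata** (simulation, complete data), percentage of trials with no computable odds ratio:

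| Comparison with pooled vehicle | n | 45% v 15%: site strata | none | 25% v 8%: site strata | none |
|---|---|---|---|---|---|
| each 0.3% arm | 12 v 12 | 48–61 | 14 | 66–76 | 39 |
| 0.1% QD | 6 v 12 | 73–83 | 17 | 85–91 | 48 |
| pooled 0.3%, all active | 24 or 31 v 12 | 24–39 | 14 | 43–57 | 37 |

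In a fuller simulation of the whole trial at 45% v 15%, the Moderate odds ratio was not computable in 0–5% of trials. On average 3.5 of the 6 single-arm odds ratios (three arms, Mild and Severe) were not computable.

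**Size when finite.** For 12 v 12 with site strata, finite odds ratios averaged 1.4–2.4 (on the log scale) against true values of 3.8–4.6.

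**Imputed data.** This check used 45% v 15%, 0.3% BID, 10% missing and 25 imputations, with simplified draws in place of predictive mean matching. All 25 datasets were finite in 43% of trials, some in 29% and none in 28%. If non-finite datasets are dropped, the pooled odds ratio averages 2.6 against a true 4.64. It is 1.9 for 0.1% QD and 4.0 for all active. Without site strata it is about 4.8. In the same check, analysing only the observed data gave a mean log odds ratio of 0.78 against 1.53, that is about 2.2 against 4.64. With equal rates (30% v 30%) the 0.3% BID and all-active results were 0.96 and 1.03, so there was no material bias.

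**The case against.** A reader might infer three stronger things, and the documents do not support them.

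*That the odds ratio usually cannot be computed.* For a 0.3% arm at the only documented rates it is close to a coin flip, and for the pooled-active comparisons it is a minority of trials. Higher failure rates depend on response rates that the documents do not give. For Severe, reaching clear or almost clear already implies at least a 3-point drop, so IGA success there is the planned primary endpoint. The 45% v 15% rates are at least for the right outcome, though not specific to that subgroup. For Mild, success requires Clear, so lower rates are plausible but still assumed.

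*That multiple imputation creates the bias.* It comes from conditioning on a finite odds ratio and is as large in observed data. Its form under imputation assumes that non-finite datasets are dropped, which the SAP does not say.

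*That nothing is left for these subgroups.* The shells still give counts, percentages and 90% and 95% Wilson intervals per arm. The observed shells provide for NE. The CMH P value does not need a finite odds ratio: for 12 v 12 it was computable in 85–92% of trials at 25% v 8%, and in 66–77% at 15% v 3%.

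It is also fair that sparse events cause part of the problem. At 25% v 8% the unstratified odds ratio still fails in 39% of trials, so removing the strata alone is not a full cure. All of these limits stand. None of them gives a reason to keep site strata in a 12 v 12 comparison.

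**Conclusion.** The point holds in limited form. Site strata within Mild and Severe raise the chance of having no odds ratio from 14% to about 48–61% for a 0.3% arm at the planning rates. For 0.1% QD the rise is from 17% to 73–83%. They also pull the finite values towards 1. The pooled-active comparisons lose less, and Moderate is little affected.

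The imputed tables have one further gap: without an NE flag or a rule for non-finite datasets, a printed odds ratio could rest on only some of the imputations.

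The sizes rest on 12–18 site groups, on subgroups filled to the cap and on assumed rates within each severity level. Smaller subgroups would make the problem worse.

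The importance is minor. This is an added subgroup analysis without multiplicity adjustment, and SAP section 4.1 makes its P values informational. The point does not concern the primary analysis or the overall IGA success analysis.

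**What to change.** In Tables 14.2.1.3.3, .4, .9 and .10, and in the matching sentence of SAP section 8.2.1:

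- Drop the pooled-site strata. Replace the odds ratio with the unstratified difference in response rates, active minus vehicle.
- In the observed-data tables, give 90% and 95% score-type intervals (Newcombe or Miettinen-Nurminen).
- In the imputed tables, pool the rate difference, which exists in every dataset. Specify a variance that stays above zero when both arms have no responders. At 15% v 3% with 12 v 12, that happens with probability 0.85^12 × 0.97^12 = 0.142 × 0.694, about 10%.
- If an odds ratio is kept, make it unstratified, add NE to .3 and .4, and print NE whenever any imputed dataset gives a non-finite value.

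The cost is SAP wording, four shells and a few lines of code. The downside is small: these tables lose site adjustment and use a different effect measure from the overall analysis.

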### Change in IGA Score Analysis

Change and percent change from baseline to Weeks 2, 4, 8, 12, and 13 in IGA score will be analyzed using descriptive summaries and an analysis of covariance (ANCOVA) with terms for treatment group, pooled site group, and baseline IGA category as covariates, by study visit. Statistical comparisons between the treatment groups will be obtained using contrasts. The least-squares (LS) means, standard errors, 90% and 95% CIs, and *P* values will be presented. These summaries will be provided for Cohort 2 subjects in the ITT population (imputed and nonimputed data) and PP population (ANCOVA using nonimputed data only). Additionally, this analysis will be repeated for Cohort 1 subjects in the All Treated population, excluding between-treatment contrasts (due to being a single-treatment cohort).

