## 3. OVERALL STUDY DESIGN AND PLAN

### 3.1. Overall Design

This is a phase 1/2b, multiple dose and 12-week, parallel group, double blind, dose ranging, vehicle-controlled study of the safety and efficacy of ARQ-252 cream 0.1% and ARQ-252 cream 0.3% in subjects with chronic hand eczema.

There are 2 cohorts of subjects:

- Cohort 1 is a multiple dose cohort in which subjects with chronic hand eczema will be assigned to ARQ-252 cream 0.3% QD x 2 weeks to be applied to both hands. Pharmacokinetics and tolerability will be evaluated.
- Cohort 2 is a parallel group, double blind, vehicle-controlled cohort in which subjects with chronic hand eczema will be randomized to ARQ-252 cream 0.3% QD, ARQ-252 cream 0.3% BID, ARQ-252 cream 0.1% QD, vehicle cream BID, or vehicle cream QD x 12 weeks to be applied to both hands. Safety and efficacy will be evaluated.

A total of approximately 6 evaluable subjects will be enrolled in Cohort 1, and a total of approximately 215 subjects will be enrolled in Cohort 2. After having met all inclusion criteria, and none of the exclusion criteria, subjects in Cohort 1 will be assigned treatment with ARQ-252 cream 0.3% QD at the Baseline visit; and subjects in Cohort 2 will be randomized in a 2:2:1:1:1 ratio (ARQ-252 0.3% QD, ARQ-252 0.3% BID, ARQ-252 0.1% QD, vehicle cream QD, or vehicle cream BID, respectively) and stratified by study site and IGA at baseline according to a computer-generated randomization list.

For subjects enrolled in Cohort 1, subject participation involves a minimum of 7 clinic visits including Screening, Baseline/Day 1, Day 2, Day 8, Day 15, Day 16, and Day 22. Subjects will be treated with investigational product (ARQ-252 cream 0.3% QD) for 2 weeks. The interval between the Screening and Baseline visits could be up to 4 weeks, therefore the anticipated maximum duration of subject participation is 7 weeks.

For subjects enrolled in Cohort 2, subject participation involves a minimum of 7 clinic visits including Screening, Baseline/Day 1, Week 2, Week 4, Week 8, Week 12, and Week 13. Subjects will be randomized to a treatment group and will be treated with investigational product for 12 weeks. The interval between the Screening and Baseline visits could be up to 4 weeks, therefore the anticipated maximum duration of subject participation is 17 weeks.

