### **3.4. Treatments Administered**

Cohort 1 will include approximately 6 evaluable subjects; all subjects are to receive ARQ-252 cream 0.3% QD.

Approximately 61 subjects will receive ARQ-252 cream 0.3% QD, approximately 61 subjects will receive ARQ-252 cream 0.3% BID, approximately 31 subjects will receive ARQ-252 cream 0.1% QD, approximately 31 subjects will receive matching vehicle cream QD, and approximately 31 subjects will receive vehicle cream BID. The randomization scheme will be 2:2:1:1:1 between these 5 treatment groups, stratified by study site and IGA at Baseline.

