P value for LS Mean Change from Baseline [2]		X.XXXX

Abbreviations: ANCOVA = analysis of covariance; CI = confidence interval; IGA = investigator global assessment; LS = least-squares; QD = once daily; SE = standard error.  
 Note: Subjects are summarized by planned treatment. IGA is a static qualitative evaluation of overall chronic hand eczema severity involving an ordinal scale with 5 severity grades (reported only in integers of 0 to 4) where 0 = Clear; 1 = Almost Clear; 2 = Mild; 3 = Moderate; 4 = Severe.  
 [1] Estimates for LS means (change from baseline), accompanying 90% and 95% CIs, and P values are from an ANCOVA with treatment group, pooled site group, and baseline IGA grade as independent variables. Baseline is the last non-missing measurement taken on or before the day of first application of study drug.  
 [2] P value for testing change from baseline is zero.  
 Reference Listing: 16.2.6.1

Table 14.2.2.1.1  
Cohort 2: Summary and Change from Baseline in Average Weekly Worst Itch – Numeric Rating Scale (WI-NRS) Pruritus Score by Study Week  
ITT Population

Study Week Statistic	Cohort 2			
	ARQ-252 Cream 0.3% QD (N=XX)	% Change	Observed	ARQ-252 Cream 0.3% BID (N=XX)
Baseline				
n	XX		XX	
Mean (SD)	XX.X (X.XX)		XX.X (X.XX)	
Median	XX.X		XX.X	
Min, Max	XX, XX		XX, XX	
Q1, Q3	XX.X		XX.X	
Week 1				
n	XX	XX	XX	XX
Mean (SD)	XX.X (X.XX)	XX.X (X.XX)	XX.X (X.XX)	XX.X (X.XX)
Median	XX.X	XX.X	XX.X	XX.X
Min, Max	XX, XX	XX, XX	XX, XX	XX, XX
Q1, Q3	XX.X	XX.X	XX.X	XX.X
Week 2				
n	XX	XX	XX	XX
Mean (SD)	XX.X (X.XX)	XX.X (X.XX)	XX.X (X.XX)	XX.X (X.XX)
Median	XX.X	XX.X	XX.X	XX.X
Min, Max	XX, XX	XX, XX	XX, XX	XX, XX
Q1, Q3	XX.X	XX.X	XX.X	XX.X

Repeat this page for the remaining study drugs (ARQ-252 Cream 0.1% QD, and Vehicle Cream (All Dose Frequencies)), showing the same study visits shown here. Then continue for Weeks 3, 4, 5, 6, 7, 8, 9, 10, 11, 12, and 13.

Abbreviations: BID = twice daily; QD = once daily; SD = standard deviation; WI-NRS = Worst Itch – Numeric Rating Scale.  

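### The Cohort 1 ANCOVAs keep a one-level treatment term and a pooled-site term that Cohort 1 cannot define, and may leave few or no residual degrees of freedom

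*SAP*

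**What the plan says.** SAP 8.2.1 (Change in IGA Score Analysis) specifies an ANCOVA "with terms for treatment group, pooled site group, and baseline IGA category as covariates, by study visit". For Cohort 1 it states that "this analysis will be repeated for Cohort 1 subjects in the All Treated population, excluding between-treatment contrasts", because that cohort has a single treatment. Only the contrasts are removed; the model terms are not.

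The Cohort 1 shell shows that this is not loose drafting. The footnote to Table 14.2.1.6.5 says that the LS means, 90% and 95% CIs and P values "are from an ANCOVA with treatment group, pooled site group, and baseline IGA grade as independent variables". The footnotes to the Cohort 1 ANCOVA tables for WI-NRS (14.2.2.1.10), HECSI (14.2.2.2.12), Pain NRS (14.2.2.3.12) and BSA (14.2.2.5.6) keep the same terms and add the baseline value of the score.

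On the cohort itself, SAP 3.4 says of Cohort 1 that "all subjects are to receive ARQ-252 cream 0.3% QD". SAP 3.2 gives the basis for its size: "Cohort 1 will include approximately 6 evaluable subjects, which is deemed adequate for the purpose of evaluating safety and PK". SAP 3.5 describes it as open label, with enrolled subjects assigned treatment and not randomized. On site pooling, SAP 6.1.6 requires that "sites should have a minimum of 10 randomized subjects", pooled within country until every treatment group is represented. It gives no separate rule for Cohort 1.

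**The concern.** A model built to compare randomized groups has been carried over to a single-arm cohort of about six. One of its terms has no variation, another has no definition that applies, and the comparison that would justify the covariates does not exist. The programmer would have to choose a site grouping, and that choice decides the residual degrees of freedom. The resulting LS mean also weights the baseline IGA grades equally by default, whatever their numbers, so it depends on which grades happen to enrol. At stake is whether the Cohort 1 intervals and P values for change from baseline mean anything, or can be computed at all.

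**Working it through.** The documents give no df, power or precision figure for Cohort 1 efficacy, so there is none to reproduce. The check is a count of model degrees of freedom.

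**Inputs**
- n = 6 (SAP 3.1 and 3.2, approximate), so 5 df after the intercept.
- Treatment levels: 1 (SAP 3.4).
- Baseline IGA levels: 1 to 3, from mild, moderate and severe (SAP 6.1.2). The 20% caps on Mild and Severe apply to Cohort 2 only (protocol inclusion criterion 4), so all three grades can occur in Cohort 1.
- Site levels: not stated for Cohort 1; taken as 1 to 6.
- Baseline-score covariate: 0 in the IGA model (8.2.1), 1 in the WI-NRS, HECSI, Pain NRS and BSA models (8.2.2, 8.2.3, 8.2.4, 8.2.6).

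**Treatment term.** With one level, the columns for intercept and treatment have rank 1 of 2. The term is aliased and uses 0 df.

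**Pooled site.** Six subjects form no group of 10, they are not randomized, and only one treatment is present. Neither pooling condition can be met within Cohort 1.

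**Residual df** = 6 − 1 − (site levels − 1) − (IGA levels − 1) − baseline score. The count assumes that site and IGA are not aliased with each other.

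| Site levels | IGA model: 1 / 2 / 3 grades | Baseline-score models: 1 / 2 / 3 grades |
|---|---|---|
| 1 | 5 / 4 / 3 | 4 / 3 / 2 |
| 2 | 4 / 3 / 2 | 3 / 2 / 1 |
| 3 | 3 / 2 / 1 | 2 / 1 / 0 |
| 4 | 2 / 1 / 0 | 1 / 0 / none |
| 5 | 1 / 0 / none | 0 / none / none |
| 6 | 0 / none / none | none |

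**t multipliers**

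| Residual df | 90% | 95% |
|---|---|---|
| 5 | 2.015 | 2.571 |
| 4 | 2.132 | 2.776 |
| 3 | 2.353 | 3.182 |
| 2 | 2.920 | 4.303 |
| 1 | 6.314 | 12.706 |
| 0 | not estimable | not estimable |

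With one site level and three grades, the IGA model gives 3.182 / 2.571 = 1.24, a multiplier 24% larger. The baseline-score models give 4.303 / 2.571 = 1.67, or 67% larger, at equal residual SD.

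**Dependence on the grade mix** (IGA model, one site level, same residual SD). The SE of the equally weighted LS mean is SD × √(Σ 1/nᵢ) / 3.
- Split 2/2/2: √1.5 / 3 = 0.408; 95% half-width 0.408 × 3.182 = 1.30 SD.
- Split 1/4/1: √2.25 / 3 = 0.500; 95% half-width 0.500 × 3.182 = 1.59 SD.
- Plain mean change: 1/√6 = 0.408; 95% half-width 0.408 × 2.571 = 1.05 SD.

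**The case against.** Several points against this are fair.

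- **The model would still run.** Software using a generalized inverse sets the aliased treatment term to zero and returns an LS mean while residual df is above 0. A reader might infer that the ANCOVA cannot be fitted at all; that goes too far. The defect is an inestimable term and an undefined one.
- **The loss of df is conditional.** A reader might also infer that the model uses up most of its 5 df. In 8.2.1 with one site level it uses 0 to 2. It reaches 3 or more only with several site levels, or with the baseline score added and three IGA grades. The 2-df and 67% figures belong to the baseline-score models, not to 8.2.1.
- **Pools might be inherited.** SAP 6.1.6 counts randomized subjects, which means Cohort 2. A Cohort 1 site that also enrols in Cohort 2 could take over its pool. The SAP does not say so, and this would add site levels and remove residual df.
- **N may exceed 6.** Six is the evaluable number. Protocol 4.2 allows unevaluable subjects to be replaced, and the All Treated population (SAP 5) counts every dosed Cohort 1 subject. With an assumed N of 8 and 3 df used, 4 remain: 2.78 against 2.36, 17% larger.
- **Covariates could reduce the residual SD.** The multipliers compare intervals at equal SD, so a narrower plain interval is likely at this size but not proven.
- **Little rests on it.** The Cohort 1 endpoint is safety, tolerability and PK (SAP 2.2.2). Its efficacy summaries were added at the sponsor's request (SAP 10), and descriptive tables of change are already planned.

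These points limit the size and the consequence. None supplies a Cohort 1 site rule or a reason to adjust a single-arm mean. The SAP itself drops the CMH test for Cohort 1 (8.1.2, 8.2.1, 8.2.2, 8.2.4) but does not reduce the ANCOVA in the same way.

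**Conclusion.** Wrong as written, low severity. All five Cohort 1 ANCOVAs contain a treatment term that cannot be estimated and a pooled-site term whose definition cannot be met within the cohort. At n = 6 the outcome ranges from harmless (one site level and one IGA grade in the IGA model, 5 df, same multiplier as a plain mean) to no SE, CI or P value (for example, three site levels and three grades in a baseline-score model). Where it falls depends on a site and IGA distribution that the documents do not give, and on N. They do not support a flat statement that the model fails or that most df are lost. They do show that the result would depend on a site grouping nobody has specified and on the enrolled mix of IGA grades. No primary or safety conclusion is affected.

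**What to change.** Delete Tables 14.2.1.6.5, 14.2.2.1.10, 14.2.2.2.12, 14.2.2.3.12 and 14.2.2.5.6, and the sentences in SAP 8.2.1 to 8.2.4 and 8.2.6 that repeat the ANCOVA for Cohort 1. In the Cohort 1 descriptive tables already planned (14.2.1.5.5, 14.2.2.1.9, 14.2.2.2.11, 14.2.2.3.11, 14.2.2.5.5), add 90% and 95% one-sample t intervals for mean change. At n = 6 these have 5 df, with multipliers 2.015 and 2.571, and need no site or IGA grouping. State the actual N in each table.

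The cost is a short SAP edit and less programming. It also removes a shell error: Table 14.2.2.5.6 is titled as an ANCOVA table but points to the descriptive shell of Table 14.2.2.2.11.
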